9.1.3. Planned Health Outcome Statistical Analyses

Table 9 Overview of Planned Health Outcome Analyses for Part C

[Endpoint / Parameter/ Display Type]	Untransformed													
	Absolute							Change from Baseline						
	Stats Analysis			Summary		Individual		Stats Analysis			Summary		Individual	
	T	F	L	T	F	F	L	T	F	L	T	F	F	L
Health Outcome - Part C: Chronic Spontaneous Urticaria Subjects														
Dermatology Life Quality Index (DLQI)				Y	Y			Y	Y		Y	Y		Y

NOTES :

- T = Table, F = Figure, L = Listing, Y = Yes display generated.
- Stats Analysis = Represents TFL related to any formal statistical analyses (i.e. modelling) conducted.
- Summary = Represents TFL related to any summaries (descriptive statistics) of the observed raw data.
- Individual = Represents FL related to any displays of individual subject observed raw data.
- Summary will be presented by dose strength, BSA and day (if applicable)

9.1.3.1. Health Outcomes Analyses/ Dermatology Life Quality Index

Planned Statistical Analyses														
Endpoint(s)														

 • Change from baseline in total and individual domain scores 														
Model Specification														

 • Endpoint will be analyzed using paired t test to compare the improvement in quality of life 														
Model Checking														

 • Refer to Appendix 8: Model Checking and Diagnostics for Statistical Analyses. 														
Model Results Presentation														

 • Estimated treatment difference and 95% confidence intervals will be presented. 														
Note: The scoring of each question is as follows:														

  
 Very much	scored 3	
 
 A lot	scored 2	
 
 A little	scored 1	
 
 Not at all	scored 0	
 
 Not relevant	scored 0	
 
 Question unanswered	scored 0	
 
 Question 7: "prevented work or studying"	scored 3	
  
 
 • The DLQI is calculated by summing the score of each question resulting in a maximum of 30 and a minimum of 0. The higher the score, the more quality of life is impaired. • The six subscores will be derived as follows: 	Very much	scored 3	A lot	scored 2	A little	scored 1	Not at all	scored 0	Not relevant	scored 0	Question unanswered	scored 0	Question 7: "prevented work or studying"	scored 3
Very much	scored 3													
A lot	scored 2													
A little	scored 1													
Not at all	scored 0													
Not relevant	scored 0													
Question unanswered	scored 0													
Question 7: "prevented work or studying"	scored 3													

Planned Statistical Analyses		
Symptoms and feelings	Questions 1 and 2	Score maximum 6
Daily activities	Questions 3 and 4	Score maximum 6
Leisure	Questions 5 and 6	Score maximum 6
Work and School	Question 7	Score maximum 3
Personal relationships	Questions 8 and 9	Score maximum 6
Treatment	Question 10	Score maximum 3

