#### **9.3.2.4. Health Outcomes Analyses**

**For CsU subjects, quality of life will be measured using the Dermatology Life Quality Index (DLQI) questionnaire.**

##### **9.3.2.4.1. Dermatology Life Quality Index**

A total score and its six individual domains (symptoms and feelings, daily activities, leisure, work and school, personal relationships, and treatment) will be calculated. Change in DLQI score from baseline in total and individual domain scores will be calculated. The mean and standard deviation of the change from baseline in total and individual domain score will be presented. The change from baseline will be analysed using the ANCOVA model including treatment, baseline and location of treatment as covariates. Point Estimates and 95% confidence intervals will be presented. More details on scoring method will be provided in RAP.

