8.1.2.2. Statistical Analysis of Pharmacokinetic Parameters

All the derived parameters described above will be listed. The first point, last point and number of points used in the determination of λ_z will be included on the listing of the derived parameters. For each of the PK parameters, except t_{max} and $\%AUC_{\infty extrap}$, the following summary statistics will be calculated for each active treatment group: median, maximum, minimum, arithmetic mean, standard deviation, coefficient of variation, geometric mean, 95% confidence interval for the geometric mean and standard deviation of logarithmically transformed data. For t_{max} and $\%AUC_{\infty extrap}$, median, maximum, minimum, arithmetic mean and standard deviation will be calculated. All statistical analysis results of these PK parameters will be presented in relation to the actual dose given (i.e. the BSA covered)

9. EXPLORATORY STATISTICAL ANALYSIS**9.1. Pharmacodynamic and Biomarker Analyses****9.1.1. Overview of Planned Pharmacodynamic Analyses**

The pharmacodynamic analyses will be based on the ‘Pharmacodynamic’ and Per-protocol populations, unless otherwise specified. All summaries will be presented by treatment group and/or include total column. Figures comparing the different treatments will be displayed overlayed where possible.

- If endpoints are listed, then all data will be listed.

[Table 6](#) provides an overview of the planned pharmacodynamic analyses, with full details of data displays being presented in [Appendix 10: List of Data Displays](#).

Table 6 Overview of Planned Pharmacodynamic Analyses for Part A

[Endpoint / Parameter/ Display Type]	Untransformed														
	Absolute							Percent of Inhibition							
	Stats Analysis			Summary		Individual		Stats Analysis			Summary		Individual		
	T	F	L	T	F	F	L	T	F	L	T	F	F	L	
Allergen Challenge - Part A : Healthy Subjects															
Weal area (mm ²)				Y	Y			Y				Y	Y	Y	Y
Weal volume (mm ³)				Y	Y			Y				Y	Y	Y	Y
Longest Weal diameter (mm)				Y	Y			Y				Y	Y	Y	Y
Weal perpendicular length (Height) (mm)				Y	Y			Y				Y	Y	Y	Y
Flare erythema ((mm ²)				Y	Y			Y				Y	Y	Y	Y

NOTES :

- T = Table, F = Figure, L = Listing, Y = Yes display generated.
- Stats Analysis = Represents TFL related to any formal statistical analyses (i.e. modelling) conducted.
- Summary = Represents TFL related to any summaries (descriptive statistics) of the observed raw data. Summary will be presented by dose strength, BSA and day (if applicable)

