
 • Change from baseline in composite total UAS7 score and components
Model Specification

 • Endpoint will be analysed using paired t test and ANCOVA to compare the treatment groups. • ANCOVA model will be fitted as: Post-Pre dose as response and pre dose as covariate.
Model Checking

 • Refer to Appendix 8: Model Checking and Diagnostics for Statistical Analyses.
Model Results Presentation

 • Estimated treatment difference and 95% confidence intervals will be presented.
Analysis of UAS7 Components

 • Analysis of UAS7 components will be performed similar to total UAS7 composite score • Summary Statistics for each component of UAS7 questionnaire will be provided by visit.
Note:

 • Composite score UAS7 will be derived using key urticaria symptoms (number of weal, Itch/Pruritus). The UAS7 score will be calculated using the summation of the 7 consecutive days sum. • Other questions collected as part of UAS7 questionnaire will be listed.

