11.8. Appendix 8: Model Checking and Diagnostics for Statistical Analyses

11.8.1. Statistical Analysis Assumptions

Endpoint(s)	
PD Parameters
Analysis	
ANOVA to estimate the effect of GSK2646264 relative to Placebo as comparison of interest. Point estimates and corresponding 95% confidence intervals will be constructed.
Analysis	
ANCOVA.
	
Distributional assumptions underlying the model used for analysis will be examined by obtaining a normal probability plot of the residuals and a plot of the residuals versus the fitted values (i.e. checking the normality assumption and constant variance assumption of the model respectively) to gain confidence that the model assumptions are reasonable.If there are any departures from the distributional assumptions, alternative models will be explored using appropriate transformed data.
Analysis	
Logistic Regression
	
Model fit will be assessed by
plotting observed probability vs predictive probabilityChi-square test for goodness fit test

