No.	Population	IDSL / TST ID / Example Shell	Title	Programming Notes	Deliverable [Priority]
5.11.	PD	Example Non-Standard_PDT 1 modified based on endpoint.	Angioedema Activity Score (AAS) – Summary Statistics (Absolute and Change from Baseline)	Absolute and Change from Baseline Part C only	SAC [1]
5.12.	PD	Example Non-Standard_PDT 2 modified based on endpoint.	Change from baseline in total Angioedema Activity Score (AAS) – Treatment Comparison	Paired t-Test (95%CI) and ANCOVA to compare treatments groups. Pre-Dose Value as Covariate Part C only	SAC [1]
5.13.	PD	Example Non-Standard_PDT 1 modified based on endpoint.	Dermatology Life Quality Index (DLQI) – Summary Statistics (Absolute and Change from Baseline)	Absolute and Change from Baseline Part C only Sum-Score and Analysis of Subscores	SAC [1]
5.14.	PD	Example Non-Standard_PDT 2 modified based on endpoint.	Change from baseline in total Dermatology Life Quality Index (DLQI) – Comparison Improvement from baseline	Paired t-Test (95%CI) Part C only No treatment comparison involved. Improvement from baseline in Quality Index	SAC [1]

Pharmacodynamic and Biomarker: Tables					
No.	Population	IDSL / TST ID / Example Shell	Title	Programming Notes	Deliverable [Priority]
Biomarker					
5.15.	PD	Example Non-Standard_PDT 1 modified based on endpoint.	Inhibition of CD69 biomarker by strength, BSA and day – Summary Statistics	Part A + C	IA[1],SAC [2]
5.16.	PD	Example Non-Standard_PDT 1 modified based on endpoint.	Relationship between Basophil Histamine (BHR) test and Weal Characteristics	Part C only No treatment comparison involved.	SAC[2]

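### Part C: the SAP's paired t-tests do not fit the parallel 3:1 design, and its DLQI plan contradicts itself and the protocol's ANCOVA on the comparison with placebo

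*SAP*

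**What the plan says.** **Design.** Protocol 3.2.1 and 5.4 make Part C a parallel comparison randomised 3:1, active to placebo; protocol 9.2 plans 16 subjects. The SAP synopsis declares Amendment 2 as its basis, and SAP 2.3 still has each subject treated bilaterally with both creams.

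**DLQI.** Protocol 9.3.2.4.1: "The change from baseline will be analysed using the ANCOVA model including treatment, baseline and location of treatment as covariates". SAP 9.1.3.1 names one method: "Endpoint will be analyzed using paired t test to compare the improvement in quality of life". Under results, the same section says: "Estimated treatment difference and 95% confidence intervals will be presented". The programming note for Table 5.14 says: "No treatment comparison involved. Improvement from baseline in Quality Index". Yet Table 5.14 is assigned shell PD_T2, to be modified for the endpoint, and that shell has a column for the mean difference from placebo with its 95% CI. Table 5.13 (shell PD_T1) summarises DLQI and its change from baseline, and Figure 5.15 plots DLQI by treatment.

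**UAS7 and AAS.** SAP 9.1.2.1 says: "Endpoint will be analysed using paired t test and ANCOVA to compare the treatment groups". SAP 9.1.2.2 and Tables 5.8, 5.10 and 5.12 say the same in substance. The ANCOVA line gives post minus pre as the response and the pre-dose value as covariate. Protocol 9.3.2.3.2 also includes location of treatment for both endpoints. SAP 2.1, which lists changes to the protocol's analysis, has two entries; one is expressly for Part A endpoints and the other for Part A dose group 2.

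**DLQI baseline.** SAP 11.3.2.1 assigns screening, as a noted exception to its rule of using the latest pre-dose value. Protocol 6.1.4 (note 12) and 6.6.1 treat screening and baseline as separate assessments and place baseline on Day 1, before dosing.

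**The concern.** A paired t-test between treatments needs both treatments observed in the same subject. That held when Part C was bilateral; it no longer does. What remains for a paired test is post-dose against pre-dose in the same person, which estimates change over time, whatever its cause: drug, vehicle, natural fluctuation or expectation.

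For DLQI this is the only method the section names. Its text, its table note, its assigned shell and the protocol cannot all be followed. A programmer who follows the table note delivers a pre/post interval in place of the protocol's adjusted comparison. For UAS7 and AAS the risk is smaller: a pre/post result could be reported under a description that calls it a comparison of groups, next to an ANCOVA that differs from the protocol's without explanation.

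**Working it through.** **Convention.** The documents give no precision figure for Part C. For Part A, protocol 9.2.1 gives 18.5 for SD 24 and n=9. Recomputed: t(0.975, 8) × 24/√9 = 2.306 × 8 = 18.45. The plan therefore uses t quantiles, and so do the figures below, in SD units with complete data.

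**Step 1: available pairs.** 16 × 3/4 = 12 active; 16 × 1/4 = 4 placebo. Subjects with both treatments: 0. The paired test between treatments has no data.

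**Step 2: what a pre/post paired test yields.** Half-width = t(0.975, n−1)/√n, in SDs of change.
- Active, n=12: 2.201/√12 = 0.64.
- Placebo, n=4: 3.182/√4 = 1.59.

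Neither interval is for active minus placebo, so neither supplies the treatment difference promised in SAP 9.1.3.1.

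**Step 3: what the descriptive DLQI output allows.** Shell PD_T1 has separate placebo and active rows with N, mean, 95% CI and SD. From these, the difference in mean change can be computed with pooled SD = √[(11·s_A² + 3·s_P²)/14] and half-width t(0.975, 14) × √(1/12 + 1/4) = 2.145 × 0.5774 = 1.24 SD. An unadjusted comparison is therefore recoverable, although no table is assigned to report it.

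**Step 4: the comparison once specified.** For change on treatment and baseline, residual df = 16 − 3 = 13. Half-width = 2.160 × 0.5774 = 1.25 residual SD, if baseline is balanced between arms. Imbalance, which is easy with 4 placebo subjects, widens it.

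**Step 5: adding location.** The documents define no levels, so their number is an assumption. With balanced covariates:

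| Location levels | df | Half-width (residual SD) |
|---|---|---|
| 2 | 12 | 1.26 |
| 3 | 11 | 1.27 |
| 5 | 9 | 1.31 |

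The cost in degrees of freedom is small. The difficulty is definition: protocol 3.1.5 lets one subject's treated area be spread over arms, legs and torso.

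**Step 6: does the version gap explain the differences?** It explains the paired test, because the parallel design came with Amendment 3. It does not explain the missing location term for UAS7: the superseded text reproduced under Amendment 3 in protocol Appendix 8 already had it.

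**Step 7: baseline.** Screening falls 28 to 7 days before Day 1, and the Day 1 DLQI looks back over the 7 days before dosing. If the screening DLQI uses the same look-back, the two describe different weeks. The SAP's own Part C schedule (11.2.1.4) already has a Day 1 DLQI.

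**The case against.** The strongest reply is that the SAP does foresee a DLQI comparison with placebo. SAP 9.1.3.1 promises the difference, and Table 5.14 uses a shell with a column for it. Section 9.1.3.1 also refers to Appendix 8, which lists "ANOVA to estimate the effect of GSK2646264 relative to Placebo as comparison of interest" for PD parameters, and the DLQI tables sit among the PD tables. SAP 9.1.1 adds: "All summaries will be presented by treatment group and/or include total column". A reader might infer from the Table 5.14 note that no DLQI comparison exists at all and that drug effect cannot be told from placebo response. The documents do not support that: the plan contradicts itself rather than uniformly excluding a comparison, and Step 3 shows an unadjusted difference can be recovered. What remains is that Appendix 8 is cited for model checking only, and no DLQI section or table specifies a model that adjusts for baseline.

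Two further inferences also go too far. Table 5.14 does not say whether its test pools the arms, and its shell is laid out by treatment, so a pooled test is not established. For UAS7 and AAS the ANCOVA line does not write out a treatment term, but the sentence before it says the purpose is to compare treatment groups; the term is reasonably understood.

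Finally, these endpoints are exploratory, nothing is formally tested, and an interval of about ±1.25 SD will settle little. That is true and limits the weight of the point. It does not justify presenting a pre/post interval in place of the comparison: protocol 9.1.1 states that the study is to estimate the effect relative to placebo with 95% CIs.

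**Conclusion.** The point holds, as a should-fix matter.

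- **DLQI:** the SAP is internally contradictory and departs from the protocol. Its only named test cannot produce the difference it promises, and no baseline-adjusted active-minus-placebo estimate with CI is specified.
- **UAS7 and AAS:** the paired t-test is not a treatment comparison in this design. The ANCOVA remains a valid one; its fault is an unrecorded omission of location.
- **DLQI baseline:** the SAP and protocol disagree.

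Specified properly, the expected 95% half-width is 1.24 SD unadjusted, or 1.25 residual SD with baseline. These figures rest on 12 and 4 subjects with complete data and, for the second, on balanced baselines. No effect size is assumed, and neither the primary safety objective nor any power statement is affected.

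**What to change.** 1. In SAP 9.1.2.1, 9.1.2.2 and 9.1.3.1 and Tables 5.8, 5.10, 5.12 and 5.14, remove the paired t-test as a treatment comparison. Pre/post change by arm may stay as description.
2. For UAS7, AAS and DLQI, write the model as change = treatment + baseline, and report active minus placebo with its 95% CI.
3. Either include location with levels defined before unblinding, or record its omission in SAP 2.1 with the reason.
4. Delete the note in Table 5.14 that excludes a treatment comparison, so that the table agrees with its text and shell.
5. In SAP 11.3.2.1, set the DLQI baseline to the Day 1 pre-dose assessment.

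The cost is SAP wording and table notes; the data are already scheduled. The one drawback is that the reported intervals will be wide, because only 4 subjects receive placebo.

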9.1.4. Overview of Planned Biomarker Analyses

The biomarker analyses will be based on the 'Pharmacodynamic' population, unless otherwise specified.

Table 10 provides an overview of the planned pharmacodynamic analyses, with full details of data displays being presented in [Appendix 10: List of Data Displays](#).

Table 10 Overview of Planned Biomarker Analyses

Endpoint / Parameter/ Display Type	Untransformed													
	Absolute							Change from Baseline						
	Stats Analysis			Summary		Individual		Stats Analysis			Summary		Individual	
	T	F	L	T	F	F	L	T	F	L	T	F	F	L
Biomarker - Part A: Healthy Subjects														
Percent inhibition of CD69 biomarker				Y			Y						Y	
Biomarker - Part C: Chronic Spontaneous Urticaria Subjects														
Percent Inhibition of CD69 biomarker				Y			Y						Y	

9.2. Pharmacokinetics and Biomarker Analyses

A potential relationship between plasma exposures of GSK2646264 (C_{min}) and changes in biomarker levels and primary endpoints will be explored graphically by plotting their respective time course profiles and systemic exposure versus response profiles. The responsibility for conducting PK-PD analyses will be CPMS. These analyses will not be part of this SAP and will be reported separately.

11.1. Appendix 1: Protocol Deviation Management and Definitions for Per Protocol Population

11.1.1. Protocol Deviation Definitions for Exclusion from predefined Populations

- Exclusions from the Study Populations should be defined prior to unblinding and should be summarized and listed [ICH E9, 1998, Section 5.2.2.] This will be included in Section 6.1 – Study Populations.
 - Exclusions from study populations may be defined as a subset of the Important Deviations as appropriate. These details should be documented in the Plan for Managing Protocol Deviations and in the RAP.
 - Any planned exclusions from study populations which are not considered to be deviations, should be defined in the RAP with rationale and any programming details as appropriate.

11.1.2. Exclusions from Per Protocol Population

A subject meeting any of the following criteria will be excluded from the Per Protocol population:

Number	Exclusion Description
01	
• Failure of any inclusion/exclusion criteria
02	
• Subjects who developed the withdrawal criteria but were not withdrawn
03	
• Any deviation that impact the safety of subjects
04	
• Failed to provide scheduled assessment
05	
• Major deviation from the conduct of trial

Protocol deviation definition criteria and resulting exclusion from analysis populations will be agreed and summarized in a separate protocol deviation definition document that has to be updated and reviewed on a regular basis.

11.2. Appendix 2: Time & Events

11.2.1. Protocol Defined Time & Events

11.2.1.1. Part A, Dose Group 1 (Healthy Volunteers)

Day:	Screening	-1	1	2	3	4	Follow-up	Notes
Visit Window (relative to Day 1)	-28 to -7						Day 5 to Day 7	
Admission to Unit		X						
Informed Consent	X							
Demographics	X							
Complete physical	X						X	
Body weight (kg)	X							
Height (cm) without shoes	X							
Brief physical		X						
Medical/medication/drug/alcohol history	X							
12-lead ECG ¹	X	X				X	X	1. Triplicate ECG at screening and CV risk factors questionnaire
Vital signs	X	X	X	X	X	X	X	
Urine drug/alcohol screen	X	X						
HIV, Hep B and Hep C screen	X							
Clinical Laboratory Tests	X	X				X	X	

CONFIDENTIAL

200196

Day:	Screening	-1	1	2	3	4	Follow-up	Notes
Visit Window (relative to Day 1)	-28 to -7						Day 5 to Day 7	
Allergen Challenge- Skin Prick Test	X ^{3,4}		X ^{3,5}		X ^{3,5}	X ⁷		3. SPT- Skin Prick Test analysis will be performed at ~15-20mins post challenge. 4. SPT with all 4 specified allergens 5. SPT using one allergen will be performed 6 hours post dose (see Clinical Trial Protocol Section 6.4.1) 7. SPT using one allergen will be performed 24 hrs after the last dose
TSH ²	X							2. TSH test only at screening only
Randomisation		X						
Tolerability Assessment				X ⁹ ←-----→				9. Tolerability assessment at pre - and ~6 hours post-dose Note: No tolerability assessment on day 4.
AE assessment		X	←-----→				X	
Concomitant Medication		X	←-----→				X	
Pharmacokinetic Blood Sample ⁶			X	X	X	X ⁸		6.PK blood sample taken at pre dose, 1, 2, 4, 8, 12 and 24hr post dose 8.PK refers to sample 24 hours post dose
Study Treatment Dosing			X	X	X			
Discharge from unit						X		
Outpatient visit	X						X	

11.2.1.2. Part A: Healthy Volunteer Time and Event Table Dose group 2

Day:	Screening	-1	1	2	3	4	5	6	7	8	Follow-up	Notes
Visit Window (relative to Day 1)	-28 to -7										Day 9 – Day 11	
Admission to Unit		X										
Informed Consent	X											
Demographics	X											
Complete physical	X										X	
Body weight (kg)	X											
Height (cm) without shoes	X											
Brief physical		X										
Medical/medication/drug /alcohol history	X											
12-lead ECG ¹	X	X								X	X	1. Triplicate ECG at screening and CV risk factors questionnaire
Vital signs	X	X	X	X	X	X	X	X	X	X	X	
Urine drug/alcohol screen	X	X										
Urine for metabolite analysis			X ¹⁰			X ²²						10. Pre dose and pool samples taken 0-12 and 12-24 hours post dose 22. Pool samples taken 0-12 and 12-24 hours post
HIV, Hep B and Hep C screen	X											
Clinical Laboratory Tests	X ¹⁷	X ¹⁷		X ⁹		X ⁹	X ¹⁷		X ¹⁷	X ¹⁷		9. Pre-dose AST, ALT, Alkaline Phosphatase, Total Bilirubin Only- : results to be communicated to the GSK Medical monitor on the same day 17.Clinical lab test as per Section 6.3.4 of the protocol

Day:	Screening	-1	1	2	3	4	5	6	7	8	Follow-up	Notes
Visit Window (relative to Day 1)	-28 to -7									Day 9 – Day 11		
Allergen Challenge- Skin Prick Test	X ^{3,4}		X ^{3,5}		X ^{3,5}	X ^{3,5}		X ^{3,7}			3. SPT- Skin Prick Test measurements will be performed ~15-20 mins post challenge. 4. SPT with all 4 specified allergens 5. SPT will be performed 6 hours post dose 7. SPT will be performed 48 hours post dose of Day 4 (on the morning of Day 6)	
TSH ²	X										2. TSH test only at screening only	
Randomisation		X										
Tolerability Assessment			X ¹¹ ←-----→ only on dosing days 1 to 4								11. Tolerability assessment at pre – and ~6 hours post-dose on dosing days	
AE assessment		X								X		
Concomitant Medication		X								X		
Pharmacokinetic Blood Sample			X ⁶	X ⁶	X ⁶	X ⁶	X ¹⁸	X ¹⁹	X ²⁰	X ²¹	6. PK blood sample taken at pre dose, 1, 2, 4, 8, 12 and 24hours post previous dose 18. PK blood sample taken at 30, 36, 48 hours, post dose of Day 4 19. PK blood sample taken at 54, 60, 72 hours, post dose of Day 4 20. PK blood sample taken at 78, 84 hours post dose of Day 4 21. PK blood sample taken at 96 hours post dose of Day 4	

Day:	Screening	-1	1	2	3	4	5	6	7	8	Follow-up	Notes
Visit Window (relative to Day 1)	-28 to -7									Day 9 – Day 11		
Blood Sample for CD69 expression			X ¹²			X ¹³	X ¹⁴		X ¹⁵	X ¹⁶		12. Predose 13. 4 hours post dose of Day 4 14. 24 hours post dose of Day 4 (sample taken in the morning of day 5) 15. 72 hours post dose of Day 4 16. 96 hours post dose of Day 4
Study Treatment Dosing ⁸			X	X	X	X						8. This will be once daily dosing using fresh bottles at 1% strength in the morning
Discharge from unit										X		
Outpatient visit	X										X	

